#### **Any cohort**

If any of the following events occur in any subject in any cohort who received at least one dose of study vaccine in the study (at any site), the site investigator will halt the vaccination of further subjects in all cohorts and the sponsor's medical monitor will be notified immediately. The sponsor's medical monitor will inform all the other investigators to halt further vaccination as well.

- Death in any subject, considered at least possibly related to the study vaccine; *OR*
- An anaphylactic reaction within 24 hours of vaccination or the presence of generalized urticaria within 72 hours of vaccination in any subject, considered at least possibly related to the study vaccine; *OR*
- A life-threatening or other serious adverse event in any subject, considered at least possibly related to the study vaccine.

#### **Cohorts 1, 2 and 3**

If any of the following events occur in any subject from Cohorts 1, 2 or 3 who received at least one dose of study vaccine in the study (across all sites), the sponsor's medical monitor will notify all investigators to halt vaccination of further subjects:

- Three or more subjects experience a severe (grade 3) (non-serious) unsolicited adverse event (of the same type) considered to be related to any of the study vaccines that persists for 3 or more days; *OR*
- Three or more subjects experience a persistent (upon repeat testing) severe (grade 3) (non-serious) abnormality (including unexplained hematuria) related to the same laboratory parameter and considered to be related to any of the study vaccines; *OR*
- Three or more subjects experience the same severe (grade 3) (non-serious) solicited systemic reaction considered to be related to any of the study vaccines that persists for 3 or more days (subjective systemic reaction corroborated by study personnel).

In case of occurrence of any of the events described above, the sponsor's medical monitor will notify the IDMC immediately. Dosing will be halted and health authorities will be notified. Within 3 business days, the IDMC will convene to review the available safety data as outlined in the charter and to discuss study suspension or discontinuation of further vaccination or to decide that vaccination may resume. The sites will be allowed to resume activities upon receipt of a written notification from the sponsor. The criteria for pausing will be re-set each time and the same criteria have to be met again to halt further vaccination.

#### **9.4. Immunogenicity Evaluations**

Venous blood samples will be collected for the determination of immune responses at the time points indicated in the [Time and Events Schedule](#). Samples for assessment of humoral immune responses will be taken from all subjects. Samples for assessment of cellular immunity will be taken from subjects at selected sites with the capabilities to process PBMC (targeted at 165 subjects [138 Ad26.ZEBOV and/or MVA-BN-Filo, and 27 placebo] in Cohort 1 and 33 subjects [28 Ad26.ZEBOV and/or MVA-BN-Filo, and 5 placebo] in each of the other cohorts). Samples to assess cellular immune responses are optional for subjects in the Cohort 1 substudy and may only be collected in a subset of subjects. Blood volumes are presented in [Table 7](#) below.

Sample collection and processing will be performed by the study-site personnel according to current versions of approved standard operating procedures. The Laboratory Manual contains further details regarding the collection, handling, labeling, and shipment of blood samples to the respective laboratories.

**Table 7: Whole Blood Volumes for Immunogenicity Assessments**

	Cohort	Humoral Immune Response (mL)	Cellular Immune Response (mL)	Approximate Total Blood Volume for Immunogenicity Assays (mL)
1	Healthy adult and elderly subjects	10	40	200 b /300/350 c
	Cohort 1 substudy subjects	10	40a	350d/360/400c,d/410c [430d/480/480c,d/530c]
2a	HIV-infected subjects	10	40	300
2b	Adolescents (12-17 years inclusive)	10	20	150
3	Children (4-11 years inclusive)			
	• 9-, 10- and 11-year old:	5	10	65
	• 6-, 7- and 8-year old:	2.5	6	36.5
	• 4- and 5-year old:	2.5	4	28.5

aThese samples are optional and may only be collected in a subset of subjects.

bOnly for subjects who do not receive a boost vaccination because of a study pause.

cSubjects in Groups 2 and 3 from Cohort 1 have an extra visit on Day 15, to assess the immune response after prime vaccination.

dIn case the pre-third vaccination blood sample coincides with the Day 365 blood sample.

\* Approximate total blood volumes including optional PBMC samples.

The immunologic assessments and purposes are summarized in [Table 8](#). The exploratory assay package may include, but might not be limited to, the listed assays.

**Table 8: Summary of Immunologic Assessments**

Sample	Purpose (non-exhaustive)
Serum, taken from all subjects (N=1,056)	
 
- Analysis of antibodies binding to EBOV GP (ELISA), possibly using different EBOV GPs
 
- Analysis of neutralizing antibodies to EBOV GP (Virus neutralization assay), possibly using different EBOV GPs
 
- Binding and/or neutralizing antibodies to adenovirus and/or MVA (Adenovirus and/or MVA ELISA and/or neutralization assay)
 
- Analysis of anti-EBOV GP, filovirus GPs and/or TAFV NP antibody characteristics, including IgG subtyping (molecular antibody characterization )
 
- ...
 

PBMC, taken from subjects at selected sites*	
 
- T-cell IFN-<math>\gamma</math> responses to EBOV GP (ELISpot)
 
- Analysis of T-cell responses to EBOV GP, filovirus GPs and/or TAFV NP (including CD4/8, IL-2, IFN-<math>\gamma</math>, TNF-<math>\alpha</math> and/or activation markers) (ICS)
 
- ...
 

IgG: immunoglobulin G; ICS: intracellular cytokine staining; IFN: interferon; IL: interleukin; TNF: tumor necrosis factor

\* (targeted at 165 subjects [138 Ad26.ZEBOV and/or MVA-BN-Filo, and 27 placebo] in Cohort 1 and 33 subjects [28 Ad26.ZEBOV and/or MVA-BN-Filo and 5 placebo] in each of the other cohorts). PBMC samples are optional for subjects in the Cohort 1 substudy and may only be collected in a subset of subjects.

## **9.5. Vaccine-induced Seropositivity**

In general, uninfected subjects who participate in Ebola vaccine studies may develop Ebola-specific antibodies as a result of an immune response to the candidate Ebola vaccine, referred to as VISp. These antibodies may be detected in Ebola serologic tests, causing the test to appear positive even in the absence of actual Ebola infection. VISp may become evident during the study, or after the study has been completed. The potential of a study participant becoming PCR-positive after vaccination is being assessed in a Phase 1 study (VAC52150EBL1002).

Subjects should not donate blood during participation in the study (from the start of screening onwards; see Sections [4.1.2](#) and [4.2.3](#)).

Consent will be obtained to contact the doctors that the subject sees regularly, to let them know that the subject is taking part in this study. It is important for all of the subject's doctors to know that the subject may be administered experimental vaccines. Subjects participating in the study will be provided with a "wallet (study) card" and instructed to carry this card with them for the duration of the study (see Section [12.3.1](#)).

## **9.6. Sample Collection and Handling**

The actual dates and times of sample collection must be recorded in the CRF or laboratory requisition form.

Refer to the [Time and Events Schedule](#) for the timing and frequency of all sample collections.

Instructions for the collection, handling, storage, and shipment of samples are found in the laboratory manual that will be provided. Collection, handling, storage, and shipment of samples must be under the specified, and where applicable, controlled temperature conditions as indicated in the laboratory manual.

## **10. SUBJECT COMPLETION/DISCONTINUATION OF STUDY VACCINE/WITHDRAWAL FROM THE STUDY**

### **10.1. Completion**

A subject will be considered to have completed the study if he or she has completed all assessments at the 6-month post-boost vaccination visit or at the Day 365 visit, whichever occurs later. A subject in the Cohort 1 substudy will be considered to have completed the study if he or she has completed all assessments at the 1-year post third vaccination visit.

### **10.2. Discontinuation of Study Vaccine/Withdrawal From the Study**

#### **Discontinuation of Study Vaccine**

If a subject's study vaccine must be discontinued before the end of the vaccination schedule, this will not result in automatic withdrawal of the subject from the study.

A subject's study vaccine (prime or boost) must be discontinued at the discretion of the investigator and after consultation with the sponsor for any of the events in Section [6.2](#).

A subject's study vaccine should be **permanently** discontinued if:

- The investigator believes that for safety reasons (eg, adverse event) it is in the best interest of the subject to discontinue study vaccine;
- The subject becomes pregnant;
- The subject has confirmed Ebola virus disease through natural exposure to the virus (eg, by travel to an affected country);
- The subject experiences any of the events described in Section [6.3](#);
- The randomization code is broken by the investigator or the study-site personnel.

Subjects meeting any of the reasons listed above must not receive any further study vaccine, but should continue to be monitored for safety and for immunogenicity according to the protocol if this does not result in safety risks for the subject. In case of early discontinuation of study vaccine due to an adverse event, the investigator will collect all information relevant to the adverse event and safety of the subject, and will follow the subject to resolution, or until reaching a clinically stable endpoint. In case of a study pause, subjects who were primed prior to the pause and did not yet receive a boost vaccination need to follow the visits as described in [Table 5](#). Once they receive the late boost vaccination, these subjects need to follow the visits as described in [Table 4](#).

## Withdrawal From the Study

Each subject has the right to withdraw from the study at any time for whatever reason. The investigator should make an attempt to contact subjects who did not return for scheduled visits or follow-up. Although the subject is not obliged to give reason(s) for withdrawing early, the investigator should make a reasonable effort to ascertain the reason(s) while fully respecting the subject's rights.

A subject will be withdrawn from the study for any of the following reasons:

- Decision by the investigator to withdraw a subject for repeated failure to comply with protocol requirements;
- Decision by the sponsor to stop or cancel the study;
- Decision by local regulatory authorities and Independent Ethics Committee (IEC)/Institutional Review Board (IRB) to stop or cancel the study;
- Lost to follow-up;
- Withdrawal of consent;
- Death.

If a subject withdraws early from the study for any of the reasons listed above (except in case of death), early withdrawal assessments should be obtained (ie, physical examination and

immunogenicity assessments for serum and PBMCs). A subject who wishes to withdraw consent from participation in the study will be offered an optional visit for safety follow-up (before formal withdrawal of consent), but the subject has the right to refuse.

If a subject is lost to follow-up, every reasonable effort must be made by the study site personnel to contact the subject and determine the reason for discontinuation/withdrawal. The measures taken to follow up must be documented.

When a subject withdraws before completing the study, the reason for withdrawal is to be documented in the CRF and in the source document. Study vaccine assigned to the withdrawn subject may not be assigned to another subject. For subjects who withdraw from the study after randomization but before the prime vaccination, an additional subject will be enrolled who will receive the same vaccination regimen as the withdrawn subject. Subjects who withdraw from the study after receiving the prime vaccination will not be replaced.

### **10.3. Withdrawal From the Use of Research Samples**

A subject who withdraws from the study will have the following options for storage of samples for potential future use:

- The collected samples will be retained and used in accordance with the subject's original informed consent for storage of samples for future use.
- The subject may withdraw consent for storage of samples for potential future use (see Section 16.2.5), in which case the samples will be destroyed and no further testing will take place. To initiate the sample destruction process, the investigator must notify the sponsor study site contact of withdrawal of consent for the storage of leftover samples for future research and request sample destruction. The sponsor study site contact will, in turn, contact the biomarker representative to execute sample destruction. If requested, the investigator will receive written confirmation from the sponsor that the samples have been destroyed. Details of the sample retention for research are presented in the ICF.

## **11. STATISTICAL METHODS**

Statistical analysis will be done by the sponsor or under the authority of the sponsor. A general description of the statistical methods to be used to analyze the safety and immunogenicity data is outlined below. Specific details will be provided in the Statistical Analysis Plan (SAP).

The primary analysis will be conducted when all subjects in Cohort 1 have completed the 6-month post-boost visit or discontinued earlier, to aid in the assessment of which vaccination schedule will be the best candidate for future studies and implementation in the field. Study-site personnel, subjects and sponsor personnel involved in subject level data review will remain blinded until the last subject in that cohort has completed the study. Sponsor personnel involved in the conduct of the primary analysis and in making future decisions for the program will be unblinded to the data of Cohort 1, but will remain blinded to the data of the other cohorts.

Interim analyses may be performed as described in Section 11.7.

The final analysis will be performed when all subjects have completed the last study-related visit or discontinued earlier (including subjects participating in the Cohort 1 substudy).

A general description of the statistical methods to be used to analyze the safety and immunogenicity data is outlined below.

Details on how to handle the data from subjects with a late boost will be described in the SAP, developed before unblinding.

Subjects who are outside the protocol-defined boost vaccination window due to a study pause and elect not to receive a late boost vaccination will not be replaced.

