**Table 3: Visit Windows**

Visit Description	Day	Window
Seven Days Post-prime Vaccination	Day 8 for all groups	±2 days
Fourteen Days Post-prime Vaccination (only in Groups 2 and 3 from Cohort 1)	Day 15 for Group 2 and Group 3	±2 days
Boost Vaccination	Day 29 for Group 1 Day 57 for Group 2 Day 85 for Group 3	±3 days
Seven Days Post-boost Vaccination	Day 36 for Group 1 Day 64 for Group 2 Day 92 for Group 3	±2 days
Twenty-one Days Post-boost Vaccination	Day 50 for Group 1 Day 78 for Group 2 Day 106 for Group 3	±3 days
Forty-two Days Post-boost Vaccination	Day 71 for Group 1 Day 99 for Group 2 Day 127 for Group 3	±3 days
Follow-up 6 Months Post-boost a	Day 209 for Group 1 Day 237 for Group 2 Day 265 for Group 3	±15 days
Follow-up 1 Year Post-prime	Day 365 for all groups	±30 days

Refer to [Table 6](#) (Section 9.1.7) for the visit windows that will be allowed for the Cohort 1 substudy.

a Subjects who completed the 6-month post-prime visit (which has been replaced with the 6-month post-boost visit per protocol Amendment 2) prior to approval of Amendment 2 were required to also attend the 6-month post-boost visit after approval of Amendment 2.

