## **11.1. Endpoints**

### **11.1.1. Primary Endpoints**

- Adverse events, collected until the 42-day post-last vaccination (excluding third vaccination) visit.
- Serious adverse events and IREs, collected from signing of the ICF onwards until the end of the study.
- Solicited local and systemic adverse events (reactogenicity), collected until 7 days after each study vaccine administration.

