Regimen*	Post-dose 1	Date and time of Dose 1 administration	Minimum of: a) 23:59 on the date of last contact (for early study discontinuations) b) 23:59 on the date of relative Day 29 Post-dose 1 c) one minute prior to Dose 2 administration d) 23:59 on the date of database cut-off (in case of interim analysis)
Post-dose 1 FU		One minute after the end of the Post-dose 1 period	Minimum of: a) 23:59 on the date of last contact (for early study discontinuation or completion) b) one minute prior to Dose 2 administration c) 23:59 on the date of database cut-off (in case of interim analysis)
Regimen*	Post-dose 2	Date and time of Dose 2 administration	Minimum of: a) 23:59 on the date of last contact (for early study discontinuation or completion) b) 23:59 on the date of relative Day 29 Post-dose 2 c) 23:59 on the date of database cut-off (in case of interim analysis) Note: subjects who do not receive Dose 2 will not have a Post-dose 2 period.
Post-dose 2 FU		One minute after the end of the Post-dose 2 period	Minimum of: a) 23:59 on the date of database cut-off (in case of interim analysis) b) 23:59 on the date of last contact (for early study discontinuation or completion)
Regimen*	Post-dose 3	Date and time of Dose 3 administration	Minimum of: a) 23:59 on the date of last contact (for early study discontinuation or completion) b) 23:59 on the date of relative Day 29 Post-dose 3 c) 23:59 on the date of database cut-off (in case of interim analysis) Note: subjects who do not receive Dose 3 will not have a Post-dose 3 period.

Post-dose 3 FU		One minute after the end of the Post-dose 3 period	Minimum of: a) 23:59 on the date of database cut-off (in case of interim analysis) b) 23:59 on the date of last contact (for early study discontinuation or completion)
-------------------	--	--	---

Note 1: * Regimen period includes both the Post-dose 1, Post-dose 2 and Post-dose 3 periods.

Note 2: FU = follow-up.

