7.1.3. Analysis Methods

In general, the AEs following vaccination will be summarized (ie, tables of descriptive statistics) by vaccination schedule and presented per period/phase. Similar summary tables will also be provided pooled by vaccine (dose).

Furthermore, unsolicited AEs will be summarized (showing number and percentage) by System Organ Class (SOC) and Preferred Term (PT). Solicited AEs (recorded by day) will be converted into the analysis format of unsolicited AEs (recorded by event) as detailed in Attachment 2. These solicited AEs will be summarized by class (local, systemic) and Preferred Term. For solicited as well as unsolicited AEs, tables focusing on severity will be created. Focus will also be on the relationship (to the study vaccine) of the solicited systemic and unsolicited AEs.

The SAEs, AEs with fatal outcome, AEs leading to permanent discontinuation from study vaccination, Grade 3 AEs and IREs will also be listed. A table summarizing all those parameters will further be created and presented per analysis period and vaccination schedule. Summary tabulations by SOC and PT for each of the category of events (ie, SAEs, AEs with fatal outcome, AEs leading to permanent discontinuation from boost vaccination, Grade 3 AEs and immediate reportable events) will also be generated on the entire reporting period. Subject narratives will be generated for these events, except Grade 3 AEs. For Grade 3 AEs, the narratives will only be generated for those AEs that are considered related to study vaccination.

For the solicited local and systemic AEs, the duration and time to first onset of the events will also be summarized. If a subject experiences more than 1 occurrence of a solicited event, the maximum duration of the events will be used. The time to first onset is defined as:

$$[\text{date of first onset} - \text{reference date} + 1]$$

The reference date is the start date of each vaccination period (ie, Post-dose 1, Post-dose 2 or Post-dose 3). Duration and time to onset of AEs will be expressed in days.

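### At the Cohort 1 six-month analysis, the whole-period SAE/IRE tables compare schedules over unequal follow-up with no person-time denominator

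*Protocol*

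**What the plan says.** Protocol section 11 sets the trigger: "The primary analysis will be conducted when all subjects in Cohort 1 have completed the 6-month post-boost visit or discontinued earlier". It gives the purpose as "to aid in the assessment of which vaccination schedule will be the best candidate for future studies and implementation in the field". SAP section 4 and Protocol 11.7 describe the same look as an interim analysis, with a final analysis after all last visits.

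Protocol 11.1.1 lists among the primary endpoints "Serious adverse events and IREs, collected from signing of the ICF onwards until the end of the study". Protocol 10.1 counts a subject as complete when "he or she has completed all assessments at the 6-month post-boost vaccination visit or at the Day 365 visit, whichever occurs later". A substudy subject is complete only after having "completed all assessments at the 1-year post third vaccination visit".

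In SAP 2.1, Table 2 closes each follow-up phase at the earlier of last contact and "23:59 on the date of database cut-off (in case of interim analysis"). SAP 7.1.3 plans two kinds of SAE/IRE summary: a table by analysis period and schedule, and tabulations by system organ class and preferred term that "will also be generated on the entire reporting period". SAP section 7 mentions no person-time denominator and no summary of follow-up length.

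Under Protocol section 5, Cohort 1 is randomized equally to three schedules until Group 3 holds 132 subjects. After that, only Groups 1 and 2 are open.

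**The concern.** At the look intended to inform the choice of schedule, subjects who entered late have not reached the end of the SAE/IRE window. These subjects are not spread evenly: after Group 3 closes, every new entrant is in Group 1 or 2. A plain percentage of subjects with an SAE or IRE, counted up to one calendar date, therefore covers different average lengths of observation by schedule. A reader of the whole-period table could take part of that difference for a difference between schedules, and the planned output gives no means of seeing how much time lies behind each percentage. The complete window is tabulated only at the final analysis, which may come after the schedule has been chosen.

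**Working it through.** **1. The plan's own visit days.** Protocol Table 3 gives the boost as "Day 29 for Group 1 Day 57 for Group 2 Day 85 for Group 3". Adding 180 days gives 209, 237 and 265, which reproduces the table's six-month post-boost days. The gap to Day 365 is 365 − 209 = 156, 365 − 237 = 128 and 365 − 265 = 100 days.

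**2. Allocation.** Stage 1 has 3 × 132 = 396 subjects. Stage 2 has 660 − 396 = 264, split equally, so Groups 1 and 2 each have 132 + 132 = 264. This matches Protocol Table 1. Half of each of Groups 1 and 2, and none of Group 3, enters in stage 2.

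**3. Model.** Assumptions: all boosts on schedule, no dropout, substudy time left out, cut-off at the trigger. Cut-off = latest value of (entry day + six-month visit day). Follow-up since prime = min(365, cut-off − entry day). Follow-up since boost = that minus 29, 57 or 85. The documents state no accrual rate, so uniform accrual over a range of durations is assumed.

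**4. One case by hand, 320-day accrual.** The cut-off is 320 + 237 = day 557. Stage 1 lasts 320 × 396/660 = 192 days. Everyone entering by 557 − 365 = day 192 has reached Day 365, so all of Group 3 has 365 days. Stage 2 entrants have between 365 and 237 days, mean 301. Groups 1 and 2 average (365 + 301)/2 = 333, a deficit of 32 days.

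**5. Range** (mean days, Groups 1 / 2 / 3):

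| Accrual (days) | Since prime | Group 3 minus Group 2 | Since boost |
|---|---|---|---|
| 30 | 266.5 / 266.5 / 273.9 | 7.4 | 237.5 / 209.5 / 188.9 |
| 90 | 277.6 / 277.5 / 299.9 | 22.4 | 248.6 / 220.5 / 214.9 |
| 180 | 311.8 / 311.6 / 350.3 | 38.7 | 282.8 / 254.6 / 265.3 |
| 320 | 333.0 / 332.8 / 365.0 | 32.2 | 304.0 / 275.8 / 280.0 |
| 365 | 337.0 / 336.7 / 365.0 | 28.3 | 308.0 / 279.7 / 280.0 |
| 730 | 351.0 / 350.8 / 365.0 | 14.2 | 322.0 / 293.8 / 280.0 |

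The largest uniform-accrual deficit shown is 38.7/350.3 = 11%. Unequal stage lengths (180 then 60 days) give 351.9 − 309.5 = 42.4 days, or 12%. Under a constant event rate, the percentage with an event shifts by roughly the same proportion. The share short of Day 365, Groups 1 and 2 against Group 3, is 76% v 52% at 180 days, 44% v 0% at 365 and 22% v 0% at 730.

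**6. When it vanishes.** With instantaneous accrual all groups have 265 days. In the 320-day case, a cut-off 128 days later gives everyone 365.

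**7. Substudy.** About 90 subjects, all in Groups 1 and 2, are followed beyond Day 365. Assuming 45 of 264 per group, cancelling a 32-day deficit needs 32 × 264/45 ≈ 188 extra days each. In the 320-day case the earliest entrant can have at most 557 − 365 = 192 by the cut-off, so the offset there is partial. Slower accrual leaves more room for it.

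**The case against.** The strongest reply is that the SAP already holds a fair comparison. SAP 7.1.3 also promises SAEs and IREs by analysis period and schedule, and Table 2 limits the post-dose 1 and post-dose 2 periods to relative Day 29. Those periods are complete for on-schedule subjects in every group before the trigger, and SAP section 7 puts its focus there. This stands, and it confines the problem to the whole-period tabulations.

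It also stands that the study is descriptive, that each schedule has its own 5:1 placebo arm in permuted blocks, and that the effect is small against sampling error. As an illustration, assume a 2% SAE risk. Among 220 vaccinees about 4 events are expected, with an exact 95% interval of 0.5% to 4.6%. An 11% relative shift is about 0.2 percentage points, or half an event.

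A reader might infer that the look is tilted against the 84-day schedule. The documents do not support that: the direction depends on the clock. Since boost, Group 1 has more follow-up than Group 3 in every scenario tried (14 to 56 days), and Group 2 ranges from 14 days less to 28 days more. The dosing pause and late boosts also make uniform accrual only a device, and SAP section 4 lets an interim analysis be merged with a later one, which could move the cut-off past the last Day 365.

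A reader might also infer that part of the primary endpoint is lost. It is not; the final analysis covers the whole window.

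What the reply does not answer is that the whole-period tables at this look would still show counts with no indication of the time observed.

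**Conclusion.** The point holds for one output: the whole-reporting-period SAE and IRE tabulations at the Cohort 1 six-month analysis. Follow-up there is incomplete and unequal between schedules. Groups 1 and 2 average less time since prime than Group 3, by about 7 to 39 days under uniform accrual of 30 to 730 days, and by at most about 12% in any pattern tried. The estimate rests on an accrual pattern the documents do not give, on-schedule boosts and a cut-off at the trigger. Substudy time reduces the deficit, and a cut-off after the last Day 365 removes it.

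It does not extend to the 28-day post-dose tables, to vaccine-placebo contrasts within a schedule, or to the final analysis of main-study follow-up to Day 365. It merits a small SAP change because this is the look meant to inform the choice of schedule.

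**What to change.** In SAP 7.1.3, keep every event up to the cut-off in the tables. For the whole-period SAE and IRE summaries add, by schedule:

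- total person-time since prime and median follow-up;
- events, or subjects with a first event, per 100 person-years;
- follow-up and events after the third vaccination, shown separately. Table 2 does not end the post-dose 2 follow-up phase at Dose 3, so that boundary has to be defined.

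Read the rates beside the 28-day tables, since a rate over the whole period is diluted by longer follow-up if events cluster soon after vaccination.

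Cutting each subject at their own six-month visit is not a good alternative. It equalises time since boost at 180 days but leaves 209, 237 and 265 days since prime, so Group 1 has (265 − 209)/265 = 21% and Group 2 (265 − 237)/265 = 11% less than Group 3. It would also move later IREs out of the tables into a listing.

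The cost is a short SAP paragraph and a little more programming. No data collection changes.
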